7.1.1.3 Patient demographics and other baseline characteristics

At Visits 1 and/or 2, data will be collected on patient characteristics including demographic information (age, sex, ethnicity, etc.) and other background or relevant medical history/ current medical condition, transfusion history, disease history, MDS classification by FAB, serum pregnancy test and vital signs.

To determine eligibility to be enrolled into the study, patients will also undergo assessments as per the inclusion and exclusion criteria which include hematology and biochemistry evaluations, hepatitis viral evaluation, serum ferritin and transferrin saturation, endogenous EPO, B12, folate, serum creatinine, creatinine clearance, ALT/AST, direct/indirect/total bilirubin, alkaline phosphatase, a known history of HIV positive test result (ELISA or Western blot) which is documented in the source documents, active Hepatitis B and/or C, serum pregnancy test and urinalysis.

Other assessments include ocular exam, audiometry and ECG.

7.1.2 Treatment period

Having completed the screening period, patients are enrolled and randomized to receive either DFX plus EPO or EPO alone. Study treatment is defined as DFX DT 10 mg/kg/day p.o. or DFX FCT 7 mg/kg/day p.o. plus EPO 40,000 units/week s.c. once weekly or EPO 40,000 units/week once weekly s.c.. EPO dose changes are allowed in both arms according to the EPO guidelines ([Appendix 3](#)). For details on study design and dose adjustments, see [Section 4.1](#). The study treatment duration is 24 weeks. After randomization, patient visits will occur weekly during the first month because key safety assessments need to be performed weekly in the first month of treatment and then every 4 weeks thereafter until week 24. In case of a dose increase of EPO after 4 weeks of treatment, an additional visit needs to be performed after 2 weeks of dose increase.

For details of assessments, see [Table 7-1](#) and [Table 7-2](#).

7.1.3 End of Treatment Visit including study completion and premature withdrawal

At the time patients discontinue study treatment, a visit should be scheduled as soon as possible, at which time all of the assessments listed for the End of Treatment (EOT) Visit will be performed. An End of Treatment CRF page must be completed, giving the date and reason for stopping the study treatment.

At a minimum, all patients who discontinue study treatment, including those who refuse to return for a final visit, will be contacted for safety evaluations during the 30 days following the last dose of study treatment.

Patients who discontinue study treatment should be considered withdrawn from the study after the final visit assessments are performed or when it is clear that the patient will not return for these assessments.

If a study withdrawal occurs, or if the patient fails to return for visits, the investigator must determine the primary reason for a patient's premature withdrawal from the study and record this information on the End of Treatment CRF page.

The Investigator must contact the IWR to register the subject's discontinuation.

For criteria for premature withdrawal see [Section 7.1.3.1](#).

[figure not shown]
7.1.3.1 Criteria for premature patient withdrawal

Patients may voluntarily withdraw from the study or be dropped from it at the discretion of the investigator at any time.

Premature patient withdrawal refers to the point/time when the patient exits from the study prior to the planned completion of all study treatment administration and/or assessments; at this time, all study drug treatment is discontinued and no further assessments are planned.

Patients who become pregnant, withdrew consent, or died must be withdrawn from the study.

Patients may be withdrawn from the study if any of the following occur:

- Unwillingness to comply with procedures as outlined in the study protocol, including unwillingness to comply with the prescribed study treatment
- Discovery of failure of randomization
- Discovery of patient ineligibility
- Intake of prohibited medications
- Adverse event(s)
- Abnormal lab value(s)
- Unsatisfactory therapeutic effect
- Protocol violation
- Lost to follow-up
- Administrative problems

Patients must be withdrawn from the study anytime when transfusion as rescue therapy is needed to ensure that all medically indicated transfusion requirements are covered, regardless of participation in the study.

7.1.4 Follow up period

All patients must have safety evaluations for 30 days after the last dose of study treatment.

Patients lost to follow up should be recorded as such on the CRF. For patients who are lost to follow-up, the investigator should show "due diligence" by documenting in the source documents steps taken to contact the patient, e.g., dates of telephone calls, registered letters, etc.

7.2 Assessment types

7.2.1 Efficacy assessments

To assess the effect of treatment with DFX combined with EPO vs. EPO alone on erythropoiesis after 12 weeks of treatment is the primary objective of this study.

Secondary objectives are to assess the effect of treatment with EPO alone on erythropoiesis after 24 weeks of treatment and to assess the effect of treatment on erythropoiesis after 24 weeks in patients that were non-responder to EPO alone after 12 weeks and switched to combination of DFX combined with EPO.

Further secondary objectives are to assess time to erythroid response and duration of erythroid response in the different treatment arms.

The efficacy parameter Hb will be assessed bi-weekly in the first month of treatment and then at every visit. Erythroid response is defined as increase in Hb ≥ 1.5 g/dL according to modified IWG 2006 criteria ([Appendix 2](#)).

The efficacy variable will be the difference in Hb from baseline vs. every month throughout the study.

To assess the effect of treatment with DFX combined with EPO on hematologic improvement within 24 weeks of treatment in patients randomized to combination therapy at baseline is one

of the secondary objectives of this study. The efficacy parameters Hb, neutrophils and platelets will be assessed bi-weekly in the first week of treatment and then at every visit. Hematological response is defined as increase in Hb, improvement of neutropenia and thrombocytopenia according to modified IWG 2006 criteria ([Appendix 2](#)). Change in hematological parameters will be assessed for all subjects on study regardless if a patient meets the required precondition as defined by IWG 2006.

Another secondary objective is to assess time to hematologic improvement in this treatment arm.

7.2.2 Safety and tolerability assessments

Safety will be monitored by hematology, blood chemistry values, regular measurement of vital signs as detailed in [Table 7-1](#) and [Table 7-2](#), as well as collection of the adverse events at every visit. For details on AE collection and reporting, see [Section 8](#).

During EPO treatment, blood pressure will be self-measured before each dose of EPO. All patients will enter the results in the patient diary. Patient diaries will not be collected by the sponsor.

7.2.2.1 Physical examination

A physical examination will be performed at Screening Visit 1, Randomization Visit and all subsequent visits except of Visit 8 which has to be performed only if EPO dose was increased at Visit 7. The physical examination at the Randomization Visit will serve as the Baseline physical examination for the entire study. The exam will entail an examination of general appearance, skin, neck (including thyroid), eyes, ears, nose, throat, lungs, heart, abdomen, back, lymph nodes, extremities and nervous system.

Information about the physical examination must be present in the source documentation at the study site.

All subjects will have standing height measured at the Screening Visit(s). This height measurement must be captured in the eCRF. Body weight will be recorded in all patients at screening, then at every clinic visit and captured in the eCRF. Weight should be measured while the patient is wearing ordinary clothing without shoes.

Significant findings that are present prior to the signing of informed consent must be included in the Relevant Medical History/Current Medical Conditions page on the patient's CRF. Significant new findings that begin or worsen after informed consent which meet the definition of an Adverse Event must be recorded on the Adverse Event page of the patient's CRF.

7.2.2.2 Vital signs

Vital signs include blood pressure and pulse measurements and will be measured at all study visits except of Visit 8 which has to be performed only if EPO dose was increased at Visit 7. After the patient has been sitting for five minutes, with back supported and both feet placed on the floor, systolic and diastolic blood pressure will be measured three times using an automated validated device, e.g. OMRON, with an appropriately sized cuff. The repeat sitting

measurements will be made at 1 - 2 minute intervals and the mean of the three measurements will be used. In case the cuff sizes available are not large enough for the patient's arm circumference, a sphygmomanometer with an appropriately sized cuff may be used. The pulse will be measured after at least 5min rest as described above by full minute assessment.

7.2.2.3 Height and weight

Height in centimeters (cm) and body weight (to the nearest 0.1 kilogram (kg) in indoor clothing, but without shoes) will be measured at the Screening Visit 1.

Weight will be measured at Screening Visit 1, Randomization Visit 3, Visit 7, 9, 10, 11, 12 and 777 (EOT).

7.2.2.4 Laboratory evaluations

Table 7-2 Clinical laboratory parameters collection plan

[figure not shown]
Test Category	Test Name
Hematology	Hemoglobin, hematocrit, white blood cell (WBC) count with differential, platelet count, red blood cell (RBC) count, mean corpuscular volume (MCV), ANC and reticulocyte count
Chemistry	Albumin, Alkaline phosphatase, ALT (SGPT), AST (SGOT), Bicarbonate, Calcium, Chloride, Creatinine, glucose, inorganic phosphorus, potassium; sodium, C-reactive protein; Creatine kinase, Direct Bilirubin, Indirect Bilirubin, Total Bilirubin, Total Cholesterol, LDL, HDL, Total Protein, Triglycerides, Blood Urea Nitrogen (BUN) or Urea, Uric Acid, gamma-glutamyl transpeptidase (GGT)
Urinalysis	Macroscopic Panel (Dipstick) (Bilirubin, Blood, Glucose, Ketones, Leukocytes esterase, pH, Protein, Specific Gravity); Microscopic Panel (examples: Bacteria, Epithelial cells, Amorphous crystals, Calcium Oxalate crystals, Uric acid crystals, Granular casts, Waxy casts, RBC casts, Casts hyaline) See complete list of Microscopic Panel in Table 14-7 .
Hepatitis markers	HBsAg, Anti-HCV, HCV PCR (Quantitative), Anti-HBs
Additional tests	Serum ferritin, Endogenous EPO, B12, folate, iron, UIBC, TIBC, FE/TIBC (TSAT), creatinine clearance, urinary protein /creatinine ratio, serum pregnancy test, urinary pregnancy test

A central laboratory will be used for analysis of all specimens collected, except urinary Dipstick analysis and urinary pregnancy tests will be performed by the local lab.

Details on the collections, shipment of samples and reporting of results by the central laboratory are provided to investigators in the [\[Laboratory Manual\]](#).

7.2.2.4.1 Hematology

Hematology samples will be collected at Screening Visits 1 and 2, Visit 3, 5, 7, 8, 9 and then at 4 week intervals, thereafter, as described in the [\[Laboratory Manual\]](#). Safety laboratory parameters monitored during the study will include Hb, hematocrit, white blood cell (WBC) count with differential, platelet count, red blood cell (RBC) count, mean corpuscular volume (MCV), ANC and reticulocyte count. All hematology samples must be sent to the central laboratory.

7.2.2.4.2 Clinical chemistry

Clinical chemistry samples will be collected at Screening Visits 1 and 2, at Randomization Visit 3 and weekly for the first four weeks of study drug administration at Visits 4, 5, 6, at Visit 7 and then at 4 week intervals, thereafter, as described in the [Laboratory Manual]. Parameters to be measured will include: albumin, alkaline phosphatase, ALT/SGPT, AST/SGOT, bicarbonate, calcium, chloride, creatinine, glucose, inorganic phosphorus, potassium, sodium, C-reactive protein, creatine kinase, direct bilirubin, indirect bilirubin, total bilirubin, total cholesterol, LDL, HDL, total protein, triglycerides, blood urea nitrogen (BUN) or urea, uric acid, gamma-glutamyl transpeptidase (GGT).

In accordance with the DFX label, serum creatinine, creatinine clearance, alkaline phosphatase, ALT/SGPT, AST/SGOT, direct bilirubin, indirect bilirubin, total bilirubin must be assessed in duplicate before the initiation of therapy to establish a reliable pre-treatment baseline.

In addition, serum creatinine, alkaline phosphatase, ALT/SGPT, AST/SGOT, direct bilirubin, indirect bilirubin, total bilirubin will be measured weekly for the first four weeks of study drug administration at Visits 4, 5, 6.

Creatinine clearance will be estimated using the Cockcroft-Gault equation. This estimate will be provided each time serum creatinine is collected.

Serum ferritin test will also be performed at Screening Visits 1 and 2 to assess the eligibility of the patient. The baseline serum ferritin value is defined as the average of the two measurements obtained during the screening period. Serum ferritin testing will also be performed monthly starting at Randomization Visit 3.

Endogenous EPO will be assessed at Screening Visit 1 to assess the eligibility of the patient.

Fe/TIBC (TSAT), B12 and Folate will be performed at Screening Visit 1 to assess eligibility to EPO treatment. Fe/TIBC (TSAT) will be additionally assessed at therapy initiation at Visit 3 and then monthly.

7.2.2.4.3 Urinalysis

Urinalysis samples will be collected at Screening Visits 1 and 2, Randomization Visit 3 and every week during the first four weeks and then every four weeks thereafter. A midstream, second voided morning urine sample will be obtained. Specific gravity, pH, blood, glucose, protein, bilirubin, ketones, and leukocyte esterase will be assessed. Microscopic analysis will be performed only in case of positive dipstick. Dipsticks will be supplied by the central lab.

At Screening Visits 1 and 2, a fresh urine sample (at least 15 ml) will be collected and sent to the central laboratory for urinary protein/creatinine ratio to assess the eligibility of the patient. In addition, urine samples for urinary protein/creatinine ratios will be collected at Randomization Visit 3 and every week during the first four weeks and then every four weeks thereafter, as described in the [Laboratory Manual]. First morning void samples must not be used for this analysis. Significant proteinuria is indicated by a urinary protein/creatinine ratio > 0.1 mg/mg.

For patients who develop proteinuria or a worsening of pre-existing proteinuria (assessed by a dipstick) at any visit, urine samples must be collected and urine protein assessed by the central laboratory.

7.2.2.4.4 Pregnancy and assessments of fertility

All female patients capable of becoming pregnant will have a pregnancy test (serum β -HCG) at Screening Visits 2 and at EOT Visit. The results of the test must be available prior to initiating treatment with any study medication. Serum pregnancy test is recommended within 48 hours prior first study drug administration. If not possible, a urine pregnancy test must also be done at Visit 3 prior to first study drug administration. Positive pregnancy tests will exclude a patient from participating in this trial.

During the treatment period, local urinary pregnancy testing will be performed monthly in all female patients capable of becoming pregnant. See [Section 8.4](#) for procedures to report pregnancy.

Pregnancy must be recorded on a Clinical Trial Pregnancy Form and reported by the investigator to the local Novartis Clinical Safety & Epidemiology Department. Pregnancy follow-up must be recorded on the same form and must include an assessment of the possible relationship to the Novartis study drug of any pregnancy outcome. Any SAE experienced during pregnancy must be reported on the SAE Report Form.

7.2.2.4.5 Hepatitis Viral tests

Hepatitis Viral testing consists of the following items: Hepatitis B Surface Antibody (Anti-HBs), Hepatitis C Antibody (Anti-HCV), Hepatitis B surface Antigen (HBsAg), HCV PCR (Quantitative). Hepatitis Viral testing will be conducted at Screening Visit 1 to assess trial eligibility.

7.2.2.5 Cardiac assessments

7.2.2.5.1 Electrocardiogram (ECG)

A standard 12 lead ECG will be performed at Screening. Interpretation of the tracing must be made by a qualified physician and documented on the ECG CRF page. Each ECG tracing should be labeled with the study number, patient initials (where regulations permit), patient number, date, and kept in the source documents at the study site. Clinically significant abnormalities present when the patient signed informed consent should be reported on the Medical History CRF page. Clinically significant findings must be discussed with Novartis prior to enrolling the patient in the study. Patients with significant cardiac abnormalities may only be enrolled if endorsed by Novartis. New or worsened clinically significant findings occurring after informed consent must be recorded on the Adverse Events CRF page.

7.2.4 Other assessments

No additional tests will be performed on patients entered into this study.

8 Safety monitoring and reporting

8.1 Adverse events

8.1.1 Definitions and reporting

An adverse event is defined as the appearance of (or worsening of any pre-existing) undesirable sign(s), symptom(s), or medical condition(s) that occur after patient's signed informed consent has been obtained.

Abnormal laboratory values or test results occurring after informed consent constitute adverse events only if they induce clinical signs or symptoms, are considered clinically significant, require therapy (e.g., hematological abnormality that requires transfusion or hematological stem cell support), or require changes in study medication(s).

Except for screening failures, adverse events that begin or worsen after informed consent should be recorded in the Adverse Events CRF. Conditions that were already present at the time of informed consent should be recorded in the Relevant Medical History/Current Medical Conditions CRF of the patient's CRF. Adverse event monitoring should be continued for at least 30 days (or 5 half-lives, whichever is longer) following the last dose of study treatment. Adverse events (including lab abnormalities that constitute AEs) should be described using a diagnosis whenever possible, rather than individual underlying signs and symptoms. When a clear diagnosis cannot be identified, each sign or symptom should be reported as a separate Adverse Event.

Severity of adverse events will be assessed as mild, moderate, or severe. Information about deaths will be collected through an EOT form.

The occurrence of adverse events should be sought by non-directive questioning of the patient (subject) during the screening process after signing informed consent and at each visit during the study. Adverse events also may be detected when they are volunteered by the patient (subject) during the screening process or between visits, or through physical examination, laboratory test, or other assessments. As far as possible, each adverse event should be evaluated to determine:

1. The severity grade (mild moderate, or severe)
2. Its duration (Start and end dates or Ongoing at End of Study)
3. Its relationship to the study treatment (Reasonable possibility that AE is related: No, Yes)
4. Action taken with respect to study or investigational treatment (none, dose adjusted, temporarily interrupted, permanently discontinued, unknown, not applicable)
5. Whether medication or therapy was given (no concomitant medication/non-drug therapy, concomitant medication/non-drug therapy)
6. Whether it is serious, where a serious adverse event (SAE) is defined as in [Section 8.2.1](#)

All adverse events should be treated appropriately. If a concomitant medication or non-drug therapy is given, this action should be recorded on the Adverse Event CRF.

Once an adverse event is detected, it should be followed until its resolution or until it is judged to be permanent, and assessment should be made at each visit (or more frequently, if necessary) of any changes in severity, the suspected relationship to the study treatment, the interventions required to treat it, and the outcome.

8.1.2 Laboratory test abnormalities

8.1.2.1 Definitions and reporting

[figure not shown]
Laboratory abnormalities that constitute an Adverse event in their own right (are considered clinically significant, induce clinical signs or symptoms, require concomitant therapy or require changes in study treatment), should be recorded on the Adverse Events CRF.

Whenever possible, a diagnosis, rather than a symptom should be provided (e.g. anemia instead of low hemoglobin). Laboratory abnormalities that meet the criteria for Adverse Events should be followed until they have returned to normal or an adequate explanation of the abnormality is found. When an abnormal laboratory or test result corresponds to a sign/symptom of an already reported adverse event, it is not necessary to separately record the lab/test result as an additional event.

Laboratory abnormalities, that do not meet the definition of an adverse event, should not be reported as adverse events. A severe event does not automatically indicate a SAE unless it meets the definition of serious as defined below and/or as per investigator's discretion. A dose hold for the lab abnormality may be required by the protocol in which case the lab abnormality would still, by definition, be an adverse event and must be reported as such.

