To estimate duration of erythroid response among responders treated with EPO alone	Duration of erythroid response is defined as the time from onset of the first response to progression/relapse (decrease in Hb \geq 1.5 g/dL from Hb value at response) among responders treated with EPO alone within the whole 24 weeks period	Refer to Section 10.5.7

Objective	Endpoint	Analysis
To estimate duration of erythroid response among responders treated with DFX+EPO	Duration of erythroid response is defined as the time from onset of the first response to progression/relapse (decrease in Hb \geq 1.5 g/dL from Hb value at response) among patients randomized to EPO+DFX up to week 24 and for patients switched from EPO to DFX+EPO from week 13 to week 24	Refer to Section 10.5.8
To evaluate tolerability and safety of the combination	Incidence of adverse events (AEs) overall and by severity, and serious adverse events (SAEs).	Refer to Section 10.5.11
To assess iron parameters in patients randomized to EPO alone, DFX+EPO and in patients randomized to EPO alone and switched to DFX+EPO after 12 weeks	Change in SF from baseline to every visit in patients throughout in the combination arm, throughout in the EPO arm and switched from EPO arm to EPO+DFX after 12 weeks	Refer to Section 10.5.9
To assess Hb parameters in patients randomized to EPO alone, DFX+EPO and in patients randomized to EPO alone and switched to DFX+EPO after 12 weeks	Change in Hb from baseline to every visit in patients throughout in the combination arm, throughout in the EPO arm and switched from EPO arm to DFX+EPO after 12 weeks	Refer to Section 10.5.10
Supportive		
To assess the effect of treatment with DFX+EPO and EPO alone on hematologic improvement within 24 weeks of treatment	Proportion of patients achieving a hematologic improvement (improvement of neutropenia and thrombocytopenia) within 24 weeks of treatment with DFX+EPO and EPO alone	Refer to Section 10.5.1
To assess the effect of treatment with DFX+EPO and EPO alone on total hematological response within 24 weeks of treatment	Proportion of patients achieving a hematological response (increase in Hb, improvement of neutropenia and thrombocytopenia) according to modified IWG 2006 criteria and patients achieving a hematologic improvement (improvement of neutropenia and thrombocytopenia) within 24 weeks of treatment with DFX+EPO and EPO alone	Refer to Section 10.5.1

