6.3.1.2 Elevations in serum creatinine

Serum creatinine should be monitored during the study as stated in the visit evaluation schedule [Table 7-1](#).

During the treatment period, patients who develop an increase in serum creatinine $\geq 33\%$ above their baseline value (average of visit 1 and 2) resulting in a serum creatinine above the upper limit of normal (ULN), on two consecutive occasions, the dose of the study drug will be reduced to 5 mg/kg/day for DFX DT and 3.5 mg/kg/day for DFX FCT until serum creatinine returns to below the age adjusted ULN.

It is recommended to check fluid balance and ensure adequate hydration of the patient.

In case of a single increase in serum creatinine, the assessment will be repeated in 2 weeks.

If after a dose reduction, a progressive increase in serum creatinine beyond the age adjusted ULN is observed, a treatment interruption is recommended.

After an interruption, if serum creatinine falls below the age appropriate ULN range on two consecutive visits, it is recommended to resume DFX DT therapy at 5 mg/kg/day or DFX FCT therapy at 3.5 mg/kg/day, and after 1 month, if the serum creatinine increase does not recur, study medication can be re-escalated to the standard dose of DFX DT at 10 mg/kg/day or DFX FCT at 7 mg/kg/day.

Caution should especially be used in patients with CrCl between 40 and less than 60 mL/min, particularly in cases where there are additional risk factors that may impair renal function such as concomitant medications, dehydration, or severe infections.

DFX therapy must be discontinued in case serum creatinine >2 times the age-appropriate upper limit or if CrCl <40 mL/min.

[figure not shown]
If after dose reduction, a progressive increase in serum creatinine is observed, Novartis must be contacted.

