6.3.1.4 Increased liver enzyme levels

If there is a persistent and progressive increase in serum transaminase levels that cannot be attributed to other causes, DFX should be interrupted. Once the cause of the liver function test abnormalities has been identified or after a return to normal levels, cautious re-initiation of DFX DT treatment at 5 mg/kg/day dose followed by dose escalation up to 10 mg/kg/day or re-initiation of DFX FCT treatment at 3.5 mg/kg/day dose followed by dose escalation up to 7 mg/kg/day may be considered. In cases of a second rise in serum transaminase levels, the investigator should contact Novartis.

[figure not shown]

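### Creatinine, creatinine-clearance and transaminase abnormalities that force a deferasirox change are automatically adverse events on DFX, but not on EPO alone, so these AE counts are not comparable between arms

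*Protocol*

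**What the plan says.** **AE definition.** Under Protocol 8.1.1 an abnormal laboratory value is an AE "only if they induce clinical signs or symptoms, are considered clinically significant, require therapy", "or require changes in study medication(s"). Section 8.1.2.1 repeats these routes and describes a dose hold as one "required by the protocol in which case the lab abnormality would still, by definition, be an adverse event and must be reported as such". It also tells sites what to leave out: "Laboratory abnormalities, that do not meet the definition of an adverse event, should not be reported as adverse events".

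**Dose rules.** Protocol 6.3.1.2 cuts the DFX dose when creatinine is at least 33% above baseline and above the upper limit of normal (ULN) on two consecutive occasions. It continues: "DFX therapy must be discontinued in case serum creatinine >2 times the age-appropriate upper limit or if CrCl <40 mL/min". Protocol 6.3.1.4 says: "If there is a persistent and progressive increase in serum transaminase levels that cannot be attributed to other causes, DFX should be interrupted". Neither section changes EPO.

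**Endpoint and tables.** The safety endpoint in Protocol Table 3-1 is "Incidence of adverse events (AEs) overall and by severity, and serious adverse events (SAEs"). Protocol 10.5.11.2 summarizes AEs by treatment group. SAP 2.10.2 also tabulates AEs that required dose adjustment or led to interruption or discontinuation.

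**Laboratory tables.** SAP 2.10.1 rests the safety assessment mainly on AE frequency and on out-of-range laboratory values. SAP 2.10.3 and its Table 2-4 apply fixed criteria to both groups for neutrophils, platelets, ALT/AST, creatinine, creatinine clearance (CrCl) and urinary protein/creatinine ratio.

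**The concern.** One of the routes by which a laboratory value becomes an AE depends on which drug the patient takes. For renal and transaminase values that route is open on DFX and closed on EPO alone. Two patients with the same central-laboratory result can then be recorded differently because of their allocation, and sites are told not to record values that fall outside the definition. The trial is open-label (Protocol 6.5.3), so the remaining judgement on EPO alone, clinical significance, is made by someone who knows the patient is not on DFX.

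The comparison affected is one the sponsor wants. The Amendment 3 rationale presents the wider CrCl limit as a way to collect renal safety data on the combination in a controlled setting. Inclusion criterion 10 may admit patients with CrCl from 40 to below 60 mL/min, close to the 40 mL/min trigger. An excess of creatinine or transaminase AEs on DFX+EPO would mix any true drug effect with the recording rule.

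**Working it through.** The plan states no figure on this point, so there is nothing to reproduce. The check is mainly textual.

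**Step 1. Which rules reach a patient on EPO alone?**

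| Source | Trigger | Acts on | Reaches EPO alone? |
|---|---|---|---|
| Protocol 6.3.1.2, reduction | Creatinine ≥33% above baseline and >ULN, twice in a row | DFX dose, mandatory | No |
| Protocol 6.3.1.2, stop | Creatinine >2 × upper limit, or CrCl <40 mL/min | DFX, mandatory | No |
| Protocol 6.3.1.4 | Persistent, progressive transaminase rise without other cause (no number) | DFX; SAP Table 4-7 code S14 lists non-interruption as a deviation | No |
| Protocol 6.3.1.8 | Unexplained cytopenia (no number) | DFX, interruption only to be considered | No |
| Protocol 6.3.1.5 | Child-Pugh B arising on study | Study treatment and participation | Yes |
| Protocol 6.1.4 | ≥50% fall from maximum response in granulocytes or platelets | Participation | Yes |
| Protocol Appendix 3, Table 14-4 | Reduced renal function | EPO starting dose only | Not on treatment |

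The asymmetry is clear for 6.3.1.2 and 6.3.1.4. It is not clear for cytopenias: the DFX rule is discretionary in the protocol (although SAP code S15 lists non-interruption as a deviation), and a separate count-based rule covers both arms.

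**Step 2. Which values are affected?** Symptoms, need for therapy and clinical significance do not depend on the arm. Only a value whose sole qualifying criterion is the DFX change is treated differently.

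**Step 3. Illustration of size.** Let r be the rate of trigger-meeting values, assumed equal in both arms. Let q be the share of them recorded as AEs on EPO alone; the share on DFX+EPO is 1. Then

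spurious difference = r − r·q = r(1 − q).

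Take n = 30 per arm (60 patients, 1:1). Take r = 5.5%, the abnormal-creatinine figure that Protocol 1.2.1.2 gives for DFX 10 mg/kg/day in a thalassemia study. Expected patients with such an AE on DFX+EPO are 30 × 0.055 = 1.65.

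| q (assumed) | Expected on EPO alone, 30·r·q | Gap r(1 − q) |
|---|---|---|
| 1 | 1.65 | 0 points |
| 0.75 | 1.24 | 1.4 points |
| 0.5 | 0.83 | 2.75 points |
| 0.25 | 0.41 | 4.1 points |
| 0 | 0 | 5.5 points |

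At r = 10% the gap is 0, 5 and 10 points for q = 1, 0.5 and 0. At r = 20% it is 0, 10 and 20 points. Neither r on EPO alone nor q is given in the documents.

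**Step 4. Do the planned laboratory tables remove the problem?** They do not depend on AE recording, which helps. Three gaps remain.

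- They leave the AE tables, the Table 3-1 endpoint, unchanged.
- Their ALT/AST criterion (>5 × ULN and >2 × baseline) is not the 6.3.1.4 trigger.
- SAP 2.10.2 splits AEs into weeks 1-12 and 13-24, but the worst-post-baseline and shift summaries in SAP 2.10.3 carry no such split. They do not say how EPO patients who switch to DFX after week 12 are grouped. The listings show both randomized and current treatment; the summaries are only said to be by treatment group.

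**The case against.** The strongest reply is that an arm-neutral comparison is already planned. SAP Table 2-4 uses one set of thresholds, including a creatinine criterion very close to the 6.3.1.2 trigger, on samples sent to a central laboratory. SAP 2.10.1 gives laboratory values a main role beside AEs. This is a pilot with no planned hypothesis test on AEs, and at the illustrated 5.5% rate the effect is at most one or two patients of 30. Most of this stands: it limits the harm and makes the repair small. It does not correct the AE tables, and it leaves the handling of switched patients open.

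Several stronger readings are tempting but not supported.

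- A reader might infer that all renal, hepatic and cytopenia rules concern DFX only. The Child-Pugh B rule (6.3.1.5) and the granulocyte/platelet rule (6.1.4) cover both arms.
- A reader might infer that such a value never counts as an AE on EPO alone. Three routes remain open, so q = 0 is only the extreme of the illustration.
- A reader might add the thalassemia rates in Protocol 1.2.1.2 (5.5% + 1.8% + 1.8% = 9.1%) and treat the total as the expected event rate. Those rates were seen on DFX in another disease. Creatinine and CrCl events overlap, because CrCl is calculated from creatinine.
- A reader might conclude that a DFX effect cannot be separated from the artefact at all. The laboratory tables allow it in part.

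**Conclusion.** The concern holds in a limited form. Creatinine, CrCl and transaminase abnormalities that trigger a DFX change are AEs by definition in DFX-treated patients. On EPO alone they become AEs only through symptoms, therapy or an unblinded judgement of clinical significance. Between-arm counts of these AEs, and of AEs requiring dose adjustment or interruption, should not be read as a comparison of toxicity.

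The direction is known: the rule can only add recorded events on DFX relative to EPO alone. The size is not. The range of 0 to 5.5 points assumes a 5.5% rate in both arms and complete recording on DFX, and it is zero if investigators record every such value on EPO alone. The contrast is cleanest in weeks 1-12, because switched EPO patients come under the DFX rules afterwards.

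**What to change.** 1. **Protocol 8.1.1 and 8.1.2.1.** State that a value meeting the numeric 6.3.1.2 criteria is recorded as an AE in either arm, whether or not a drug is changed. The criteria are creatinine ≥33% above baseline and >ULN on two consecutive occasions, creatinine >2 times the upper limit, or CrCl <40 mL/min. This cannot be extended to 6.3.1.4 or 6.3.1.8, which give no number to apply uniformly.
2. **SAP 2.10.2 and 2.10.3.** Present the existing Table 2-4 renal, ALT/AST, neutrophil and platelet criteria by randomized arm for weeks 1-12, before EPO patients switch to DFX. Name that table as the between-arm comparison for these harms.

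The AE tables should not be repeated without laboratory events that led to a DFX change. That would remove combination-arm events that are also symptomatic or clinically significant, keep their EPO-arm equivalents, and could hide real DFX toxicity.

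The cost is one sentence in the protocol, one extra table from data already collected, and a few more laboratory AEs recorded on EPO alone. No test or patient is added, and no dose or clinical rule changes. Tables of AEs requiring dose adjustment will still depend on which drug is taken and should be read descriptively.
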